3.3 Exploratory Objectives and Endpoints

OBJECTIVES	ENDPOINTS (OUTCOME MEASURES)
Exploratory	
Evaluate the clinical efficacy of convalescent plasma administration as compared to active drug (e.g., Remdesivir) recipients in DMID Protocol Number: 20-0006 or other relevant COVID-19 Protocols	
 • Clinical Severity 
 ○ Ordinal scale: 
 ■ Time to recovery, defined by time to levels 1-3 on the ordinal scale ■ Time to an improvement of one category and two categories from Day 1 using an ordinal scale. ■ Participant clinical status using ordinal scale at Days 3, 5, 8, 11, 15, 22, and 29. ■ Mean change in the ordinal scale from Day 1 to Days 3, 5, 8, 11, 15, 22, and 29.

 ○ National Early Warning Score (NEWS): 
 ■ Time to discharge or to a NEWS of ≤ 2 and maintained for 24 hours, whichever occurs first ■ Change from Day 1 to Days 3, 5, 8, 11, 15, and 29 in NEWS. 	NEWS assessed daily while hospitalized and on Days 15 and 29.

 ○ Oxygenation: 
 ■ Oxygenation free days to Day 29. ■ Incidence and duration of new oxygen use during the study. 	Days of supplemental oxygen (if applicable)

 ○ Non-invasive ventilation/high flow oxygen: 
 ■ Non-invasive ventilation/high flow oxygen - free days to Day 29. ■ Incidence and duration of new non-invasive ventilation or high flow oxygen use during the study. 	
 • Days of non-invasive ventilation (if applicable). • Days of high flow oxygen (if applicable).

 ○ Invasive Mechanical Ventilation / extracorporeal membrane oxygenation (ECMO): 
 ■ Ventilator / ECMO free days to Day 29. ■ Incidence and duration of new mechanical ventilation or ECMO use during the study. 	
 • Days of invasive mechanical ventilation (if applicable). • Days of ECMO (if applicable).

OBJECTIVES	ENDPOINTS (OUTCOME MEASURES)

Evaluate the virologic efficacy of convalescent plasma as assessed by:
 
 Percent of participants with detectable SARS-CoV-2 in OP or ET samples at Days 3, 5, 8, 11, and 15. Quantitative SARS-CoV-2 in OP or ET samples at Days 3, 5, 8, 11, and 15. Qualitative SARS-CoV-2 in OP or ET samples at Days 3, 5, 8, 11, and 15. 	
 Quantitative and Qualitative PCR for SARS-CoV-2 in OP or ET swab at Day 1; Days 3, 5, 8, and 11 (while hospitalized) and Days 15, if available.

Evaluate the timing and titer of anti-SARS-CoV-2 antibody responses after convalescent plasma administration
	
 Plasma antibody binding and neutralization on Day 1 (prior to plasma administration); Days 3, 8, 15, 29, and visit Day 60.

Evaluate the timing and quality of SARS-CoV-2 cellular responses after convalescent plasma administration
	
 Cellular responses in whole blood on Day 1 (prior to plasma administration); Days 3, 8, 15, 29, and visit Day 60.

Evaluate the change in inflammatory responses with convalescent plasma administration
	
 Plasma and cellular markers of inflammation on Day 1 (prior to plasma administration); Days 3, 8, 15, 29, and visit Day 60.

Evaluate the change in clinical status by 8-point ordinal scale and/or NEWS with change in inflammatory markers
	
 Ferritin, C Reactive Protein, D-Dimer, Fibrinogen, Erythrocyte Sedimentation Rate, Triglycerides, IL-6 on Study Day 1, 3, 5, 8, 11, 15, 29 (when available).

Evaluate the safety of convalescent plasma administration as compared to active drug (e.g., Remdesivir) recipients in DMID Protocol Number: 20-0006
 
 Cumulative incidence of Grade 3 and 4 clinical and/or laboratory AEs through Day 29. 
Changes in WBC with differential, hemoglobin, platelets, creatinine, glucose, total bilirubin, ALT, AST, and PT over time (analysis of lab values in addition to AEs noted above).
	
 SAEs Grade 3 and 4 AEs 
WBC with differential, hemoglobin, platelets, creatinine, glucose, total bilirubin, ALT, AST, and PT on Day 1; Days 3, 5, 8, and 11 (while hospitalized); and Days 15 and 29 (if attends in-person visit or still hospitalized).


Compare the safety of plasma plus standard care vs. standard care alone by cumulative incidence of serious adverse events by day 60
	
 SAEs

4 STUDY PLAN

4.1 Study Design

80 participants will be enrolled and randomized. All participants will be followed through Study Day 60. The study population will consist of adults >18 years of age hospitalized, intubated and mechanically ventilated with confirmed COVID-19 pneumonia caused by SARS-CoV-2.

This randomized, controlled, open-label, phase 1 trial will assess the safety and efficacy of convalescent plasma in severely ill, hospitalized participants with pneumonia due to COVID-19. This study will enroll adults over the age of 18, including pregnant women.

A total of 80 eligible participants will be randomized 1:1 to either receive standard care and 2 units of convalescent plasma collected from ABO-compatible donors who have recovered from COVID-19 or standard care alone. Participants in the treatment arm will receive convalescent plasma on Study Day 1 in addition to standard care. Participants will be assessed daily while hospitalized through Study Day 29. Participants discharged from the hospital will be asked to attend remaining study visits at Study Days 15, 22, 29, and 60. The Study Day 22 visit may be conducted by phone. All participants will undergo a series of safety, efficacy, and laboratory assessments. Blood samples will be collected on Days 1 (prior to plasma administration), 3, 5, 8, 11, 15, 29, and 60. Oropharyngeal or endotracheal samples will be collected as possible on Days 1 (prior to plasma administration), 3, 5, 8, 11, and 15. Given the COVID-19 restrictions and the difficulty some of the participants might have to attend an in person visit after hospital discharge, the collection of Day 60 data for primary and secondary endpoints and the collection of Day 60 research samples for exploratory tests may be performed up to 90 days following the Day 60 visit.

4.2 Scientific Rationale for Study Design

This randomized, open-label trial is intended to evaluate the effect of treatment with convalescent plasma in hospitalized COVID-19 patients. There are no data from randomized, controlled trials demonstrating clinical benefit for any therapies for COVID-19. Further, there are no randomized, controlled studies of passive immunotherapy for coronavirus related disease, including SARS, MERS, and COVID-19. Thus, quality evidence from controlled trials is valuable.

The current standard of care for COVID-19 patients is unclear and in flux. Several treatment options are recommended for COVID-19 patients as per Departmental or Hospital system guidelines, but none are FDA-approved nor supported by strong clinical trials evidence. Given the potential severity of disease in COVID-19 patients and the limited validated treatment options available, the study will include hospital system- or medical provider-directed standard of care treatments in both treatment and control arms, including experimental or non-FDA approved therapeutics.

There are three possible benefits of a plasma infusion that may be unrelated to any binding of SARS-CoV-2 viruses by antibodies in the plasma:

- Volume load
- Oncotic load

- Fc binding – The Fc of the antibodies (the non-virus binding end of the antibody) present in plasma (both influenza and other antibodies) will bind to receptors in the body. This binding may modulate the immune response. It is for this reason that IVIG (concentrated antibody preparations) is sometimes used in autoimmune diseases. Volume load would have the largest effect. This volume effect could be beneficial, though a volume load in an ill population may also increase the risk to the subject.

Nonimmune plasma was considered as a placebo, but there may be cross-reactive antibodies in this plasma that would complicate analysis and/or nonspecific immune modulating effects from Fc binding. A half-normal saline with albumin was entertained as a better physical representation of study plasma, but this approach has several shortcomings. First, the albumin will provide oncotic pressure, i.e., it would not be a true inactive placebo. Second, the sequential labeling in the blood bank would be difficult to replicate on this compound, and therefore the labeling would be able to distinguish placebo from active plasma. Therefore, it would still need to be masked. Finally, identification of plasma donor without recent COVID-19 is challenging, given the limited availability of serologic assays to disprove recent infection. Thus, many asymptomatic donors may have recently been infected COVID-19 and their plasma would not serve as a control.

Given the potential for increased risk with a saline control, and the inability to effectively blind the study (discussed below) immune plasma will be compared with standard care (i.e., there is no comparator infusion, saline or other). If a treatment effect is determined to exist, then subsequent studies can dissect the components of the treatment effect (volume load, Fab binding of virus, Fc binding with immune modulation, and oncotic pressure).

This study is not blinded. Saline or other controls would be significantly different in appearance compared to plasma. Plasma needs to be distributed from blood banks. However, hospital blood banks do not have the capabilities of distributing placebo. Conversely, pharmacies could not distribute the study plasma. Hospitals have systems for double-checking administration of blood products, as well as documentation of the administration of blood products in the hospital record (paper or electronic). Mechanisms for documentation of administration of a study drug would not be sufficient for documentation of a blood product, and the mechanisms for documentation of plasma products would not be amenable to documentation of a blinded study product. Therefore, effectively blinding the study, wherein there is high likelihood that the investigative team does not know whether the participant received plasma or saline, was not felt to be practical.

Participants will be randomized in a 1:1 ratio. Higher ratios were considered (i.e., 2:1 or 3:1 active:control); however this would hamper the assessment of the control rate of the various efficacy assessments, making planning future confirmatory studies difficult.

4.3 Justification for Dose

Plasma volume in adults can be estimated by multiplying actual body weight in kilograms by 40 mL/kg. [19] For 70-kg person, the plasma volume would be estimated to be 2800 mL (40 mL/kg x 70 kg).

Standard plasma dosing is 2 units, (~200-250 mL per unit). At the discretion of the principal investigator, patients less than 90kg or with concern for volume overload, may receive 1 unit of plasma.

The volume of a unit of plasma is 200-250 mL. Therefore, the study dose of 2 units of plasma could be equal to as much as 500 mL. A plasma volume of 500 mL at an anti-SARS-CoV-2 titer of 1:160 would increase the titer in the plasma to approximately 1:25; then fall to 1:13 after equilibration with the extravascular space.

The dose of anti-SARS-CoV-2 antibodies needed to modify COVID-19 clinical disease is not known. The range of anti-SARS-CoV-2 titers in individuals who have recovered from COVID-19 is not fully characterized; in the recently described cohort of 5 patients receiving convalescent plasma, anti-SARS-CoV-2 titers ranged from 1:1,800 to 16,200 by ELISA for IgM and ELISA for IgG, and 1:80 to 1:480 to neutralizing antibody (Shen JAMA 2020). A second observational description of convalescent plasma in China identified ten donors. In their cohort of 40 plasma donors, 39 had neutralizing antibody titers >1:160, while a single donor had titers of 1:32, as determined by plaque reduction assay (Duan PNAS 2020).

In Influenza studies, Rockman et al demonstrated in a H5N1 model in ferrets, that achieving a HI titer of 1:8 with a hyperimmune IVIG without any other antivirals was sufficient in preventing death if given early in the illness (during fever), and in delaying death if given at the onset of severe disease. [20]

4.4 End of Study Definition

A participant is considered to have completed the study if he or she has completed all phases of the study including the Day 60 visit shown in the Schedule of Activities (SoA), [Appendix 12.1](#). Given the COVID-19 restrictions and the difficulty some of the participants might have to attend an in person visit after hospital discharge, the collection of Day 60 data for primary and secondary endpoints and the collection of Day 60 research samples for exploratory tests may be performed up to 90 days following the Day 60 visit.

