- Percent of participants with detectable SARS-CoV-2 in OP or ET samples at Days 3, 5, 8, 11, and 15.
- Quantitative SARS-CoV-2 in OP or ET samples at Days 3, 5, 8, 11, and 15.
- Qualitative SARS-CoV-2 in OP or ET samples at Days 3, 5, 8, 11, and 15.

Evaluate the timing and titer of anti-SARS-CoV-2 antibody responses after convalescent plasma administration

- Plasma antibody binding and neutralization on Day 1; Days 3, 8, 15, 29, and 60

Evaluate the timing and quality of SARS-CoV-2 cellular responses after convalescent plasma administration

- Cellular responses in whole blood on Day 1; Days 3, 8, Days 15, 29, and 60

Evaluate the change in inflammatory responses with convalescent plasma administration

- Plasma and cellular markers of inflammation on Day 1; Days 3, 8, 15, 29, and 60

Evaluate the change in clinical status (by clinical severity score) to the change in inflammatory markers

- Ferritin, C Reactive Protein, D-Dimer, Fibrinogen, Erythrocyte Sedimentation Rate, Triglycerides, IL-6 on Study Day 1, 3, 5, 8, 11, 15, 29, and 60 (when available).

Study Population: Severely-ill, hospitalized adults ≥ 18 years old with COVID-19 pneumonia

Phase: Phase I

Enrolling Sites: This is a single site study conducted in the Hospitals of the University of Pennsylvania.

Description of Study Intervention: This open label, randomized, controlled, phase I study will assess the administration of 2 units of convalescent plasma collected from ABO-compatible donors who have recovered from COVID-19. Participants will be randomized 1:1 to receive either convalescent plasma on Study Day 1 in addition to standard care or standard care alone.

Study Duration: We expect the study to last 6 months from initiation

Participant Duration: An individual participant will complete the study in about 60 days, from screening at Day -1 or 1 to follow-up on Day 60 ± 5 days

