7 STUDY INTERVENTION DISCONTINUATION AND PARTICIPANT DISCONTINUATION/WITHDRAWAL

Participants will be considered to have completed the study if they are followed through Study Day 60 (+ 90 days) and complete the final study visit (or followed through to death at or before 60 days).

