8.1.1.1 Screening Procedures in Pregnant Women

To best understand risk and benefit of study enrollment for pregnant women, we will follow this SOP for consideration of enrollment.

Standard Operating Procedure for Pregnant Patients:

1. Maternal Fetal Medicine (Obstetrical service managing pregnant patients) consults Infectious Diseases
2. Obstetrics (OB) and Infectious Diseases (ID) study physicians discuss possible enrollment in study, considering factors including fetal gestational age, maternal co-morbidities, severity of COVID-19 disease, volume status.
3. Discussion between OB, ID, patient (if possible) and patient legally authorized representative on risks and benefits of study.
4. With enrollment and plasma administration: close observation in acute setting (eg, in COVID-19 unit, ICU or Labor & Delivery)
5. Continue close monitoring after plasma administration. Participants will be followed through the 60 days of the study. Data will not be collected after the Day 60 visit nor will data be collected on neonates.

The volume of venous blood to be collected is presented in [Table 2](#).

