8.3 Safety and Other Assessments

Study procedures are specified in the SOA. A study physician licensed to make medical diagnoses and listed on the 1572 will be responsible for all trial-related medical decisions.

- Physical examination: A symptom-directed (targeted) physical examination will be performed at screening and when needed to evaluate possible adverse event(s) (i.e. any new symptoms). No physical exam is needed for routine study visits.
- Clinical laboratory evaluations:
 - Fasting is not required before collection of laboratory samples.
 - Blood will be collected at the time points indicated in the SOA. Clinical laboratory parameters include WBC, differential, Hgb, PLT, Creatinine, glucose, total bilirubin, AST, ALT, and PT.
 - This testing will be performed at each clinical trial site in real time.

Table 2: Venipuncture Volumes¹

	Screen	Baseline							
Day +/- Window	-1 to 1	-1 to 1	3±1	5±1	8±1	11±1	15±2	29±2	60±5
Type and screen	X 10 mL								
Safety hematology, chemistry, liver tests		X 10 mL	X 10 mL	X 10 mL	X 10 mL	X 10 mL	X 10 mL	X 10 mL	
Blood for plasma/serum and cells, including research assays		X 32 mls	X 32 mL		X 32 mL		X 32 mL	X 24 mL	X 32 mL

Total volume	10 mL	42 mL	42 mL	10 mL	34 mL	10 mL	42 mL	34 mL	32 mL
Total volume all study days									264 mL

1 See SOE for specific tests to be performed.

2 Total volume calculated assumes no routine clinical laboratory results that can be used for the screening, baseline, and safety laboratory values.

3 Samples may be collected for up to 90 days following the Day 60 visit.

8.3.1 *Procedures to be Followed in the Event of Abnormal Laboratory Test Values or Abnormal Clinical Findings*

If a physiologic parameter (e.g., vital signs, or laboratory value) is outside of the protocol- specified range, then the measurement may be repeated once if, in the judgment of the investigator, the abnormality is the result of an acute, short-term, rapidly reversible condition or was an error. A physiologic parameter may also be repeated if there is a technical problem with the measurement caused by malfunctioning or an inappropriate measuring device (i.e., inappropriate-sized BP cuff).

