4. Expectedness to study treatment or process – [Unexpected – if the event severity and/or frequency is not described in the investigator brochure (if applicable) or protocol].
5. Action taken with respect to study or investigational treatment or process (none, dose adjusted, temporarily interrupted, permanently discontinued, unknown, not applicable)
6. Whether medication or therapy taken (no concomitant medication/non-drug therapy, concomitant medication/non-drug therapy)
7. Whether the event is serious

Once an adverse event is detected, it should be followed until its resolution or until it is judged to be permanent, and assessment should be made at each visit (or more frequently, if necessary) of any changes in severity, the suspected relationship to the study treatment, the interventions required to treat it, and the outcome.

For this study, all Grade 3 and 4 AEs, all SAEs occurring from the time the informed consent is signed through the Day 60 visit will be documented, recorded, assessed, and reported. In addition, any grade 1 or 2 or higher hypersensitivity reaction is also reported as an AE.

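### Research samples labelled Day 60 may be drawn as late as about Day 150 to 155, and no analysis rule uses the actual sampling day

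*Combined protocol and SAP*

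**What the plan says.** **Visit window and late allowance.** The synopsis (section 1.1) describes "follow-up on Day 60 ± 5 days", and Table 2 and Table 4 carry the same ±5 days. Section 4.4 says that collecting Day 60 data and research samples "may be performed up to 90 days following the Day 60 visit". Sections 4.1 and 8.1.2 and note 10 to Table 4 repeat this. Note 3 to Table 2 says the same of blood: "Samples may be collected for up to 90 days following the Day 60 visit".

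**Immune and inflammatory endpoints.** Section 3.3 lists plasma antibody, cellular responses and markers of inflammation by nominal day, with Day 60 the last. Section 9.4.9 plans means, SDs and confidence intervals, or medians for skewed data. It adds descriptive trends, mixed models where appropriate, and further detail in the SAP. It does not say whether time is nominal or actual.

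**SAEs.** Section 3.3 has an exploratory endpoint, the "cumulative incidence of serious adverse events by day 60". Section 8.4.4 says that "all SAEs occurring from the time the informed consent is signed through the Day 60 visit will be documented". Section 8.4.5.1 instead runs adverse event reporting to study completion, and section 7 counts participants as complete if they are "followed through Study Day 60 (+ 90 days) and complete the final study visit". Section 8.1.1.1, on pregnant participants, says "Data will not be collected after the Day 60 visit".

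**The concern.** A blood sample shows the participant's state on the day it is drawn. A late phone call can recover what had happened by Day 60, but a late sample cannot. Without a rule on actual time, a value drawn around Day 150 may be summarised with values drawn near Day 60.

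Day 60 is the last immune time point in the plan. Section 2.3.1.4 raises the possibility that plasma could reduce the size or duration of protective immunity and says that this should be investigated. The late immune data are the natural place to look. If late attendance differs by arm, which can happen in an open-label trial, different sampling times could mimic or hide a difference between arms.

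The SAE question is smaller. If events are captured until a late final contact and no onset cut-off applies, participants seen late contribute more time at risk to a figure labelled Day 60.

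**Working it through.** The plan states no figure that depends on this point, so there is none to reproduce.

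**1. Range of sampling days.** The inputs are Day 60 ± 5 (section 1.1, Tables 2 and 4) and the 90-day allowance (section 4.4).

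- Earliest: 60 − 5 = Day 55.
- Latest, counting 90 days from the visit as section 4.4 words it: 55 + 90 = Day 145 to 65 + 90 = Day 155.
- Latest, counting 90 days from nominal Day 60 as section 7 reads: 60 + 90 = Day 150.
- Spread: 155 − 55 = 100 days, against 65 − 55 = 10 days inside the window. Ratio of latest to earliest: 155/55 = 2.8.

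**2. What a delay could do to a decaying marker.** The half-life is an assumption. With exponential decay, the fold difference is 2^(delay / half-life).

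| Assumed half-life (days) | 10-day delay | 90-day delay | 100-day delay |
|---|---|---|---|
| 14 | 1.6 | 86 | 141 |
| 28 | 1.3 | 9.3 | 12 |
| 60 | 1.1 | 2.8 | 3.2 |
| 90 | 1.1 | 2.0 | 2.2 |

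The ±5-day window is therefore tolerable across this range, and the 90-day allowance is not.

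**3. What unequal lateness could do to an arm comparison.** Assume identical true kinetics in both arms, with 30% of one arm and 10% of the other sampled 90 days late. The apparent ratio of geometric means is 2^((0.30 − 0.10) × 90 / half-life).

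- Half-life 28 days: 2^(0.20 × 3.21) = 2^0.64 = 1.6.
- Half-life 60 days: 2^(0.20 × 1.5) = 2^0.30 = 1.2.

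If lateness is equal across arms, this bias is zero. What remains is extra scatter and a wrong time label.

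**4. SAE windows side by side.**

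- Section 8.4.4 ends capture at the Day 60 visit. Taken literally, that is Day 55 to 65.
- Section 8.4.5.1 ends it at study completion. With section 7, that can be Day 150.
- Section 8.1.2 lets late Day 60 clinical data come from existing records or a phone call, and calls them retrospective.
- Section 8.4.3.1 records start and stop dates for each reported event. Section 9.4.4 plans proportions at Day 60 and a time-to-first-event curve.
- No section says that onsets after Day 60 are left out of the Day 60 count.

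If later events were counted, the reported incidence would be p + s(1 − p)q. Here p is the true Day 60 incidence, s the share of participants seen at the full 90-day limit, and q the chance of a first SAE in the extra 90 days. All three are assumed.

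- p = 0.30, s = 0.10, q = 0.05: 0.30 + 0.10 × 0.70 × 0.05 = 0.3035.
- p = 0.30, s = 0.50, q = 0.20: 0.30 + 0.50 × 0.70 × 0.20 = 0.37.
- With an onset cut-off at Day 60, the excess is zero.

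**The case against.** The strongest reply concerns SAEs. A reader might infer that the Day 60 incidence necessarily mixes follow-up of about 55 to 155 days. The documents do not support that. Section 8.1.2 describes late retrieval of Day 60 information, onset dates are recorded, and the 90 days follow the visit; they do not move it. Longer SAE follow-up arises only if sections 7 and 8.4.5.1 are read together against section 8.4.4. This reply stands, and it reduces the SAE point to reconciling text.

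On samples, the reply is that section 9.4.9 already mentions mixed models and leaves detail to the SAP, so it is not established that late values will be averaged as Day 60. That is fair, but a mixed model on nominal days has the same fault, and the text does not call for actual time.

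It is also true that simple decay may overstate the effect. The endpoint includes the participant's own antibody, and the worked example in section 4.3 puts the transfused contribution at only about 1:13 after equilibration. The fold differences above are therefore illustrations, not predictions. That lateness will differ by arm is likewise a possibility that the documents do not show.

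A reader might also infer that every primary and secondary endpoint ends at Day 29, so that the late-collection text is wrong to name either. That holds for the primary endpoints only. Survival time, duration of hospitalization and new respiratory support during the study have no Day 29 cap in section 3.2.

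**Conclusion.** The point on samples holds. Values sharing the Day 60 label can be up to 100 days apart, and neither section 3.3 nor section 9.4.9 says to use the actual day. How much this matters depends on marker kinetics, the share sampled late and any imbalance between arms, none of which the documents give.

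The SAE point is secondary. Sections 7, 8.4.4 and 8.4.5.1 must be reconciled. On the less favourable reading, an assumed 30% incidence would be reported as 30.35% to 37%; on the other reading there is no excess.

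The affected endpoints are exploratory. The primary safety and primary efficacy endpoints are fixed at Day 29, and no sample size, power or error rate changes. This is a cheap improvement, not a flaw that threatens the trial's main conclusions.

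**What to change.** 1. In section 9.4.9 and the SAP, restrict the nominal Day 60 summary of antibody, cellular and inflammatory values to samples within Day 60 ± 5. Keep later samples and analyse them by actual days since Day 1, for example in a mixed model with actual time.
2. Report by arm the number of late samples and the distribution of sampling days.
3. State in section 8.4.4 and the SAP that the exploratory Day 60 SAE incidence counts events with onset on or before Study Day 60, whatever the date of contact, using the recorded onset dates. Reconcile sections 7, 8.4.4 and 8.4.5.1.
4. Reconcile section 8.1.1.1 with the late-collection text.
5. In that text (sections 4.1, 4.4 and 8.1.2, and note 10 to Table 4), remove only the reference to primary endpoints. Keep the reference to secondary endpoints, because some run past Day 29.

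The cost is wording, plus fewer samples in the nominal Day 60 summary; no sample is discarded. The collection date of each sample is needed. Section 8.2.1 leaves sample storage to the manual of procedures, so it should be confirmed that this date is recorded.
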